### **9.6 Additional Study Restrictions**

The following additional restrictions will be in place for the duration of the study:

- Subjects must abstain from alcohol during the 24 hours prior to screening and the 24 hours prior to admission until 48 hours post-final IMP dose
- Subjects should refrain from eating food containing poppy seeds for 48 hours prior to screening and for 48 hours prior to admission until 48 hours post-final IMP dose
- Subjects must not take part in any unaccustomed strenuous exercise from the 72 hours before the screening visit and then from 72 hours prior to admission until discharge from the study
- Subjects must not donate blood or plasma (outside of this study) from clinical unit admission, throughout the study duration, and for at least 30 days following last dose of study medication

The additional restrictions above are not exclusion criteria; if non-compliance occurs, the Sponsor will be contacted and each deviation will be assessed on a case by case basis.

## **10 Study Procedures**

Study procedures will be performed as detailed in the study schedule of assessments [Appendix 2](#) (Part 1) and [Appendix 3](#) (Part 2), and in accordance with Quotient's SOPs unless otherwise stated in this protocol.

## **10.1 Screening**

Within the 28 days preceding first dose all subjects will be required to undergo screening procedures. Screening procedures will be carried out in accordance with the schedule of assessments in [Appendix 2](#) (Part 1) and [Appendix 3](#) (Part 2).

If the start of the study is delayed for any reason so that the interval between screening and first dose exceeds 28 days all or part of the screening procedures will be repeated at the discretion of the investigator.

Screening safety procedures such as safety bloods, ECGs, vital signs, urine alcohol, urine cotinine, urine drug screen and urinalysis can be repeated as clinically indicated under the discretion of the investigator or sub-investigator if there is a concern regarding a subject's safety or eligibility to participate in the trial.

### **10.1.1 Subject Re-Screening**

This study permits the re-screening of a subject who has discontinued the study as a pre-treatment failure (i.e., subject has not been randomized); the reason for failure must be temporary and expected to resolve. If re-screened, the subject must be re-consented.

## **10.2 Admission and Pre-dose Procedures**

The identity of the subjects will be confirmed at admission and pre-dose.

In addition, the ongoing eligibility of subjects will be re-assessed at admission/pre-dose, as described in [Sections 9.2](#) and [9.3](#).

Admission/pre-dose safety procedures such as safety blood tests, ECGs, vital signs, urinalysis and drugs of abuse tests can be repeated as clinically indicated under the discretion of investigator or sub-investigator if there is a concern regarding a subject's safety or eligibility to participate in the clinical trial.

Alternative subjects for the first dose occasion, in any cohort, will not require admission procedures to be repeated if dosing is within 2 days of their prior admission.

If dosing is delayed, subjects who have completed admission procedures do not need admission procedures to be repeated if dosing is within 2 days and the subjects have remained resident in the clinical unit.

The admission and pre-dose procedures are presented in [Appendix 2](#) (Part 1) and [Appendix 3](#) (Part 2).

## **10.3 Study Day Procedures**

### **10.3.1 Blood Volume**

The total blood volume for each subject will not exceed 550 mL in an 8-week period (based on a representative healthy subject weighing at least 110 pounds). See the study Lab Manual for further details on sample volumes and collection and processing requirements. The number and timing of samples may be amended following review by the Sponsor and/or SAC.

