Based on the maximum allowed escalations and anticipated PD activity, the highest anticipated dose will be 12600 µg. Using the NOAEL of 18 mg/kg in monkeys, the HED-based safety factor is approximately 32. With the predicted human PK at 12600 µg (assuming 70kg patients and 90% SC bioavailability), the dose-based, concentration (Cmax)-based, and exposure (AUC)-based safety factors are estimated to be 100, 231, and 24, respectively.

Doses administered will be predicted not to exceed a mean Cmax of 103,950 ng/mL and a mean AUC(0-24h) of 1,775,000 ng.h/mL, which is the sex-averaged mean NOAEL exposure limits after the first dose of 18 mg/kg in the cynomolgus NOAEL 28-day good laboratory practice (GLP) toxicology study, in any individual subject.

The non-clinical program, containing pharmacology, PK, PD, and toxicology data of PDM608, supports the initiation of a human clinical study for the treatment of neurodegenerative diseases.

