#### **Baseline Characteristics**

5. Healthy men or non-pregnant, non-lactating healthy women of non-childbearing potential
6. Body mass index (BMI) of 18.0 to 33.0 kg/m^2 as measured at screening
7. Weight ≤100 kg at screening

Inclusion criterion 5 from the list above will be re-assessed at admission/pre-dose on Day 1.

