#### **Diagnostic Assessments**

6. Evidence of current SARS-CoV-2 infection or exposure to confirmed infection within 10 days prior to the first dose of study drug
7. Clinically significant abnormal clinical chemistry, hematology or urinalysis as judged by the investigator (laboratory parameters are listed in [Appendix 1](#)). Subjects with Gilbert's Syndrome are allowed
8. Positive hepatitis B surface antigen (HBsAg), hepatitis C virus antibody (HCV Ab), human immunodeficiency virus (HIV) antibody results or positive tuberculosis (TB) screening test
9. Evidence of renal impairment at screening, as indicated by an estimated creatinine clearance (CLcr) of <90 mL/min using the Cockcroft-Gault equation
10. Subjects with a QTcF interval of >450 msec at screening or first admission. At screening, QTcF will be based on a single 12-lead ECG; this single ECG can be repeated once if parameters are outside the limits for confirmation. At admission, this value will be from the mean of triplicate values
11. Positive highly sensitive serum pregnancy test at screening or highly sensitive urine pregnancy test at first admission. Those who are pregnant or lactating will be excluded

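### The 550 mL blood-volume ceiling is based on a subject of at least 110 lb, but the eligibility criteria set no minimum weight, so Sections 9.2 and 10.3.1 do not match.

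*Combined protocol and SAP*

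**What the plan says.** Section 10.3.1 (Blood Volume) applies one ceiling to everybody and gives its basis in the same sentence: the total for each subject "will not exceed 550 mL in an 8-week period (based on a representative healthy subject weighing at least 110 pounds"). Individual sample volumes are left to the Lab Manual, and the number and timing of samples may be amended by the Sponsor and/or the safety advisory committee.

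Section 9.2 (Inclusion Criteria, Baseline Characteristics) controls body size by two criteria. Criterion 6 is "Body mass index (BMI) of 18.0 to 33.0" kg/m². Criterion 7 is "Weight ≤100 kg at screening". Neither states a minimum weight.

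Three exclusions in Section 9.3 could bear on light subjects:
- Criterion 9 excludes an "estimated creatinine clearance (CLcr) of <90 mL/min using the Cockcroft-Gault equation". Body weight enters that equation, which is set out in Section 13.6.1.
- Criterion 5 concerns poor venous access and has no weight element.
- Criterion 26 is a general judgement of fitness by the investigator and gives no weight threshold.

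No section gives a separate blood-volume limit for lighter subjects.

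**The concern.** The ceiling covers every subject, but the reason given for it covers only those of 110 lb or more. If the eligibility criteria admit people below that weight, the protocol's stated basis does not hold for part of its own population, and the volume permitted per kilogram is highest in the smallest people.

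The ceiling is the only volume limit in the protocol, and sampling is not fixed. Sections 12 and 13.6.2 allow PK, PD and antibody sampling to be changed or extended, and Section 13.11 allows extra safety samples at any point. What is at stake is protection of participants who, according to Section 6.6.3, can expect no clinical benefit. No endpoint, estimate or test depends on it.

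**Working it through.** **Inputs.** Ceiling 550 mL in 8 weeks and basis weight 110 lb (Section 10.3.1). BMI floor 18.0 kg/m² and weight of at most 100 kg (Section 9.2). CLcr exclusion below 90 mL/min (Section 9.3, criterion 9). Cockcroft-Gault equation (Section 13.6.1). The 550 mL figure cannot be rebuilt, because per-draw volumes are only in the Lab Manual. What can be checked is whether eligibility guarantees the basis weight.

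**Step 1: the basis weight in kilograms.** 110 × 0.4536 = 49.9 kg.

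**Step 2: the height above which the BMI floor guarantees it.** The lowest eligible weight at height h (in metres) is 18.0 × h². Setting this equal to 49.9 gives h = √(49.9 / 18.0) = 1.665 m. Anyone shorter than about 166.5 cm can meet the BMI criterion below 110 lb.

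**Step 3: lowest weight allowed by BMI, and the ceiling per kilogram (550 / weight).**

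| Height | Lowest weight at BMI 18.0 | Ceiling per kg |
|---|---|---|
| 165 cm | 49.0 kg (108 lb) | 11.2 mL/kg |
| 160 cm | 46.1 kg (102 lb) | 11.9 mL/kg |
| 155 cm | 43.2 kg (95 lb) | 12.7 mL/kg |
| 150 cm | 40.5 kg (89 lb) | 13.6 mL/kg |

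At the basis weight the ceiling is 550 / 49.9 = 11.0 mL/kg. At 155 cm the excess is 12.7 / 11.0 = 1.15, or about 15%. The heights are illustrative; the documents give no height distribution.

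**Step 4: does the renal exclusion close the gap?** Solving Cockcroft-Gault for the highest serum creatinine that still gives a CLcr of 90 mL/min:

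maximum creatinine = (140 − age) × weight × (0.85 if female) / (72 × 90)

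At 43.2 kg:
- man aged 30: 110 × 43.2 / 6480 = 0.73 mg/dL
- woman aged 30: 0.73 × 0.85 = 0.62 mg/dL
- woman aged 50: 90 × 43.2 × 0.85 / 6480 = 0.51 mg/dL
- woman aged 65: 75 × 43.2 × 0.85 / 6480 = 0.43 mg/dL

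At 45 kg the limits are 0.76 mg/dL (man aged 30), 0.65 (woman aged 30) and 0.53 (woman aged 50). A light subject must therefore have a fairly low creatinine to enter, and increasingly so with age. The criterion thins out the group but sets no minimum weight.

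**The case against.** The strongest reply has three parts.

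First, 550 mL is a ceiling and not a planned draw. With the sample volumes in the Lab Manual, nothing in the documents shows that the scheduled samples come near it. A reader might infer that light subjects will actually have 550 mL taken. The documents do not support that; 12.7 mL/kg is what would be permitted at that weight. This part stands and limits the size of the point.

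Second, BMI is not the only filter. The CLcr exclusion bears hardest on light people. Women must also be post-menopausal or permanently sterile (Section 9.4), which plausibly moves eligible women toward the ages where the creatinine limit is tightest. The investigator can also decline anyone judged unfit. This stands as a reason to expect few such subjects. It does not remove the mismatch, since none of these criteria states a weight.

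Third, the 110 lb figure describes a representative subject, so it may explain where the ceiling comes from without being meant as an entry requirement. That is a fair reading, and it is why a weight floor should not be treated as already implied. It still leaves a limit applied to each subject on a basis that not every eligible subject meets.

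A reader might also be tempted to extend the point to dosing: the doses are flat, and the margins for the top anticipated dose in Section 6.2 are worked out at 70 kg ("With the predicted human PK at 12600 µg (assuming 70kg patients and 90% SC bioavailability"), so the missing weight floor might seem to undermine them. The documents do not support that step. Section 6.2 states its 70 kg assumption openly. Sections 6.2 and 8.2.2 contain a separate rule capping predicted exposure. The difference also comes from using a 70 kg reference with flat doses, not from the missing floor: scaling simply by weight, a 50 kg minimum would still give an HED-based factor of about 32 × 50 / 70 = 23 in place of 32.

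**Conclusion.** The inconsistency is real and small. Section 10.3.1 justifies its ceiling for subjects of at least 110 lb, and Section 9.2 allows lighter ones below about 166.5 cm. In the 155 cm illustration the ceiling per kilogram is about 15% above its value at the stated basis.

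This rests on BMI 18.0 being the only size-based lower bound, on the subject passing the CLcr exclusion, and on dividing the full ceiling by body weight. How many such subjects would enroll, and how much blood they would give, cannot be determined from the documents. The point is a minor one of participant protection and leaves the statistical analysis untouched.

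**What to change.** Reconcile Sections 9.2 and 10.3.1 by one of two routes:
- state in inclusion criterion 7 a minimum weight consistent with the basis of the blood-volume limit; or
- state in Section 10.3.1 a limit that expressly covers lighter eligible subjects.

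Which route to take, and what value to set, is for the sponsor and investigator.

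Either is a short text edit. The first may make a few light volunteers ineligible, a small loss in a healthy-volunteer study. The second keeps them eligible but needs a check of the Lab Manual volumes against whatever limit is stated. No analysis section needs to change.

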### 10.3.2 Timing of Procedures

There are times where the protocol requires more than one procedure to be completed at the same time point. In these instances, the following will apply to post-dose time points:

- ECGs should be taken prior to vital signs when both measurements are scheduled at the same time point.
- PK/PD samples should take priority (i.e., taken at the nominal time point) over other procedures scheduled at the same time point.
- Other assessments (e.g., physical examinations) will be performed within the required time windows.

As guidance, the preferred order of assessments is:

All safety assessments will be timed and performed relative to the start of dosing.

### 10.3.3 Discharge from the Clinical Unit

Subjects will be discharged from the clinical unit following completion of study-specific procedures as detailed in [Appendix 2](#) (Part 1) and [Appendix 3](#) (Part 2). However, the investigator may ask a subject to remain domiciled for additional safety observation and monitoring (e.g., as indicated for an AE).

### 10.3.4 Return Visits

Subjects in Part 1 and Part 2 will be required to return to the clinical unit at specified time points for the assessments described in [Appendix 2](#) (Part 1) and [Appendix 3](#) (Part 2); the acceptable deviations for the return visit are also described in these appendices.

### 10.3.5 Medical Supervision

A physician will be responsible for the clinical aspects of the study and will be available at all times during the study.

### 10.3.6 Follow-up

If a subject reports any AEs that can present a cause for concern, they will be required to attend the clinical unit for a further follow-up assessment (as an unscheduled visit) and will be followed up until the AE has resolved. Completion of the last scheduled return visit or unscheduled follow-up call/visit will be considered the end of the study.

## 11 Dosing of Subjects

### 11.1 Food and Fluid Intake

Subjects will be allowed water up to 1 hour before each scheduled dosing time and will be provided with 240 mL of water at 1 h post-dose (to ensure adequate hydration).

Thereafter, water will be allowed ad libitum after 1 h post-dose. Decaffeinated fluids will be allowed ad libitum from lunch time on the day of dosing.

The calorie/fat content of meals are not required to be controlled. Subjects will be provided with a standardized menu. See also the food and liquid restrictions detailed in [Section 9.6](#). Meals will be provided at appropriate times.

### **11.2 Dosing Compliance**

Subjects will be observed by study staff during all clinical phases of the study to assure compliance to all study procedures including dose administration.

Doses will be administered by trained staff to ensure dosing compliance.

The date and time that each subject is dosed will be recorded in the subject's eCRF. Any violation of compliance will require evaluation by the investigator and Sponsor to determine if the subject can continue in the study.

### **11.3 Prior and Concomitant Medications**

No prescribed medications, over-the-counter medications or herbal remedies will be permitted from 14 days or 5 half-lives (whichever is longer) before IMP administration until a subject's final visit except HRT, up to 4 g per day of acetaminophen, and those deemed necessary by the investigator to treat AEs (see also [Section 9.3](#)). Any medications used will be recorded in the eCRF.

No COVID-19 vaccines will be permitted within 14 days prior to first dose until a subject's final visit on this trial. COVID-19 vaccinations are not acceptable concomitant medications.

Emergency equipment and drugs will be available within the clinical unit as per current standard procedures. In the unlikely event that they are required, their use will be documented.

## **12 Pharmacokinetic and Pharmacodynamic Blood Sampling**

Venous blood samples for analysis by a bioanalytical lab for PK and PD analysis will be collected from the subjects by a trained member of the clinical team.

Samples will be sent for laboratory testing in linked anonymized form (subject number only). This information can be linked directly to the subject by the Quotient research team and study monitor but not by the laboratory staff or Sponsor.

Venous blood samples will be withdrawn via venipuncture according to the Schedule of Assessments presented in [Appendix 2](#) (Part 1) and [Appendix 3](#) (Part 2). The acceptable deviations from the nominal blood sampling times are detailed in the schedules.

The timing and number of the samples may be amended by the Sponsor and/or SAC, including collection over a longer duration. Any changes to blood sampling time points will be documented and retained in the TMF.

Samples will be collected into appropriate tubes as specified by the bioanalytical laboratory. Details of sample tubes and processing will be contained in the Clinical Sample Processing Manual (CSPM).

Pharmacodynamic parameters analyzed by the bioanalytical lab may include the following:

- Immunophenotyping by flow cytometry to determine numbers/percentages of the following immune cells:
  - Total T cells (CD45+CD3+)

- Helper T cells (CD45+CD3+CD4+CD8-)
- Cytotoxic T cells (CD45+CD3+CD4-CD8+)
- Regulatory Helper T cells (CD45+CD3+CD4+CD8-CD25+Foxp3+)
- Regulatory Cytotoxic T cells (CD45+CD3+CD4-CD8+CD25+Foxp3+)
- Macrophages (CD45+CD14+CD11b+)
- Dendritic cells (CD45+CD123+HLA-DR+CD11c+)
- Cytokine analysis:
  - Panel 1: IL-1 $\alpha$ , IL-1B, IL-1RA, IL-12/IL-23p40, IFN- $\alpha$ 2a, MCP-1
  - Panel 2: IL-1 $\beta$ , IL-6, IL-10, IL-12p70, IFN- $\gamma$ , GM-CSF, TNF- $\alpha$

As described in [Section 6.4](#) Pharmacodynamic Rationale, a subset of the safety hematology labs (WBC, monocyte, and eosinophil values) will be analyzed as an indicator of pharmacodynamic activity to aid in defining the maximum dose level to be administered to subjects in this trial.

## 13 Assessment of Safety

### 13.1 Definition and Classification of Adverse Events

An AE is any untoward medical occurrence in a subject that occurs either before dosing (referred to as a pre-dose AE) or once a medicinal product has been administered, including occurrences that are not necessarily caused by or related to that product.

An adverse drug reaction (ADR) is any AE where a causal relationship with the IMP is at least a reasonable possibility (possibly related or related).

AEs will be monitored from the time the subject signs the ICF until 30 days after the final dose of study drug. The severity of AEs should be assessed as follows:

Mild	An AE that is easily tolerated by the subject, causes minimal discomfort and does not interfere with everyday activities
Moderate	An AE that is sufficiently discomforting to interfere with normal everyday activities; intervention may be needed
Severe	An AE that prevents normal everyday activities; treatment or other intervention usually needed

### 13.2 Assessment of Causality

Every effort should be made by the investigator to try to explain each AE and assess its relationship, if any, to the IMP. The temporal relationship of the event to IMP administration should be considered in the causality assessment (i.e., if the event starts soon after IMP administration and resolves when the IMP is stopped).

Causality should be assessed using the following categories:

Unrelated:	Clinical event with an incompatible time relationship to IMP administration and that could be explained by underlying disease or other drugs or chemicals or is incontrovertibly not related to the IMP
Possibly related:	Clinical event with a reasonable time relationship to IMP administration that is unlikely to be attributed to concurrent disease or other drugs or chemicals
Related:	Clinical event with plausible time relationship to IMP administration that cannot be explained by concurrent disease or other drugs or chemicals

The degree of certainty with which an AE is attributed to IMP administration (or alternative causes such as natural history of the underlying disease or concomitant therapy) will be determined by how well the experience can be understood in terms of one or more of the following:

- Known pharmacology of the IMP
- Reactions of a similar nature have been previously observed with the IMP or this class of drug
- The experience being related by time to IMP administration, terminating with IMP withdrawal or recurring on rechallenge
- Alternative cause

### 13.3 Recording Adverse Events

AEs will be recorded from the time of providing written informed consent until 30 days after the last dose of study drug. During each study visit the subject will be questioned directly regarding the occurrence of any adverse medical event according to the schedule in eCRF. All AEs, whether ascribed to study procedures or not, will be documented immediately in the subject's eCRF. This will include the date and time of onset, a description of the AE, severity, seriousness, duration, actions taken, outcome and an investigator's current opinion on the relationship between the study drug and the event. A diagnosis and final opinion on the relationship between the study drug and the event will be provided at the end of the study by the investigator.

Any subject who withdraws from the study due to an AE will be followed until the outcome is determined and written reports are provided by the investigator.

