**Duration of Study:**

In Part 1 (SAD), subjects will receive a single administration on one occasion. The estimated time from consent until the follow-up visit is 7 weeks.

In Part 2 (MAD), subjects will receive multiple administrations (4 doses) across a period of 4 weeks (once weekly dosing). The estimated time from consent until the follow-up visit is 13 weeks.

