## Appendix 2      Schedule of Assessments: Part 1 Single Ascending Dose

Study Day →	SCRN	D -1	D1				D2	D3	D4	D5	D6	D7	D8	D11	D15	D22	Premature
		Admit	Pre-Dose	0H	1H	3H	12H	24H	48H	72H	96H	120H	144H	168H	240H	336H	504H
Window →	D-28 to -2	Day of	1H j	n/a	±10M	±10M	±1H	±2H	±2H	±2H	±2H	±2H	±2H	±24H	±24H	±24H	
Assessments ↓																	
Informed Consent	X																
Medical History	X	X a															
Weight, Height, BMI	X	X b															
Vein Assessment	X	X															
Urine Alcohol, Cotinine, Drug Screen	X	X															
Serum Pregnancy	X c																
Urine Pregnancy		X d															
Randomization			X e														
IMP Administration f				X													
Physical Exam	X							X		X			X				X
Hem & Chem m	X	X						X	X	X		X		X		X	X
Virology & TB Test	X																
FSH g	X																
CLcr	X							X	X	X		X		X		X	X
Urinalysis	X		X k					X	X	X	X	X	X				
Single ECG	X	X													X	X	X
Triuplicate ECG			X		X	X	X	X	X	X	X	X	X				

Study Day →	SCRN	D -1	D1				D2	D3	D4	D5	D6	D7	D8	D11	D15	D22	Premature
		Admit	Pre-Dose	0H	1H	3H	12H	24H	48H	72H	96H	120H	144H	168H	240H	336H	504H
Window →	D-28 to -2	Day of	1H j	n/a	±10M	±10M	±1H	±2H	±2H	±2H	±2H	±2H	±2H	±24H	±24H	±24H	
Assessments ↓																	
Vital Signs h	X	X	X				X	X	X	X	X	X	X				X
PK			X		X	X	X	X	X	X	X	X	X	X	X	X	X
PD			X				X			X			X	X	X	X	X
ADA			X										X		X	X	X
Adverse Events									X								
Concomitant Medications									X								
Clinical Residency			Clinical Residency admit Day -1, discharge Day 8											RV	RV	RV	

RV = Return Visit

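### Part 1: adverse events are to be recorded to Day 31, but the last scheduled visit is Day 22, so the available text shows no scheduled contact for nominally the last 9 days of the window

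*Combined protocol and SAP*

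**What the plan says.** Two sections set the adverse event window, and both apply to Part 1 without qualification. Section 13.1: "AEs will be monitored from the time the subject signs the ICF until 30 days after the final dose of study drug". Section 13.3: "AEs will be recorded from the time of providing written informed consent until 30 days after the last dose of study drug".

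Section 13.3 also says when subjects are asked: "During each study visit the subject will be questioned directly regarding the occurrence of any adverse medical event according to the schedule in eCRF". The eCRF schedule it refers to is not among the documents.

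The Part 1 schedule in Appendix 2 gives a single dose on Day 1 and a residential stay ("Clinical Residency admit Day -1, discharge Day 8"), followed by return visits on Days 11, 15 and 22. Day 22 is labelled 504H. The only later column is for premature discontinuation.

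For Part 1 the synopsis says: "The estimated time from consent until the follow-up visit is 7 weeks". Section 10.1 fixes the screening interval: "Within the 28 days preceding first dose all subjects will be required to undergo screening procedures".

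Section 10.3.6 covers what happens after the scheduled visits. Follow-up beyond them starts with the subject: "If a subject reports any AEs that can present a cause for concern, they will be required to attend the clinical unit". Otherwise participation closes with the schedule: "Completion of the last scheduled return visit or unscheduled follow-up call/visit will be considered the end of the study".

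**The concern.** The recording window and the visit schedule end on different days. For the first three weeks after dosing, subjects are resident or are seen at return visits and questioned. After Day 22 the window remains open for more than a week, but nothing in the text available brings site and subject into contact unless the subject makes a report.

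Incidence of adverse events is part of the primary endpoint (Section 7), and treatment-emergent events will be tabulated as counts and percentages (Section 14.4). If those tables follow the window in Sections 13.1 and 13.3, they will combine a solicited period with a shorter period that rests on volunteered reports, and the second is likely to be less complete. Section 14.4 leaves further detail of the safety analyses to the Reporting and Analysis Plan. That plan can choose a window, but it cannot supply answers to questions that were never asked.

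**Working it through.** **Inputs**
- Part 1 dosing: one dose, Day 1 (synopsis; Appendix 2).
- Window: 30 days after the last dose (Sections 13.1 and 13.3).
- Last scheduled Part 1 visit: 504 hours after dosing (Appendix 2).
- Screening: up to 28 days before the first dose (Section 10.1).
- Consent to follow-up visit, Part 1: 7 weeks (synopsis).
- Return-visit window: ±24 hours. Its application to Day 22 is an assumption, because the window row in the extracted table is not fully aligned with its columns.

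**Step 1: reproduce the plan's own duration.** Days after dosing at the last visit = 504 / 24 = 21, which is study Day 21 + 1 = 22. Adding the screening limit gives 28 + 21 = 49 days, and 49 / 7 = 7.0 weeks. This matches the synopsis exactly, so Day 22 as the final Part 1 visit does not rest on the reading of one table column.

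**Step 2: end of the window.** Day 1 + 30 = Day 31. A contact on that day would come 28 + 30 = 58 days after the earliest consent, and 58 / 7 = 8.3 weeks. The stated 7 weeks does not reach it.

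**Step 3: the gap.**

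| Last visit held on | Days from visit to Day 31 | Share of the 30 days |
|---|---|---|
| Day 21 (24 h early) | 31 − 21 = 10 | 10/30 = 33.3% |
| Day 22 (nominal) | 31 − 22 = 9 | 9/30 = 30.0% |
| Day 23 (24 h late) | 31 − 23 = 8 | 8/30 = 26.7% |

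**Step 4: does other text close the gap?**
- Section 8.3 lets a phone call count as the last contact, but schedules none.
- Section 8.2.1 lets the Safety Advisory Committee or the Sponsor change safety time points on emerging data. This is a permission, not a plan.
- Sections 12 and 13.6.2 allow PK, PD and antibody sampling to be extended, again as a permission.
- Section 10.3.6 provides unscheduled follow-up, triggered by the subject's own report.
- Sections 13.4.1, 13.5 and 15.3.1 set no day limit on reporting serious events or events of special interest, but the reporting clock starts when the site becomes aware.

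None of these schedules a contact between Day 22 and Day 31.

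The adverse event row of Appendix 2 is a merged cell that did not survive extraction, and Figure 1 is not shown. Neither is used here.

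**The case against.** The strongest reply is that a recording window may properly be longer than the visit schedule. Sections 13.1 and 13.3 say that events are monitored and recorded for 30 days. They do not promise that every subject will be asked about Day 31. Relying on subjects to report after their last visit is a recognisable design, and Section 10.3.6 brings back those with a concerning event. This stands in part: the passages are not in flat contradiction. But the only mechanism that Section 13.3 gives for finding events is questioning at visits, and the reader is not told that it stops 9 days before the window does.

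The second reply is that the eCRF schedule, which is not available here, may contain a later query. The synopsis duration fixes the last visit but does not exclude a later call. This stands as a limit and is the main reason for medium confidence.

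The third reply is that no passage plans an incidence over 30 days. Section 14.4 does not define the treatment-emergent window, and the safety analysis is descriptive. This also stands, and it limits the harm to completeness of the data.

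A reader might also infer that Part 2 has the same fault, because its visits run to Day 60 while its window ends on Day 52 (Day 22 + 30). The documents do not support that. Scheduled visits continue past the end of the Part 2 window, so none of its 30 days lacks a later visit. How events with onset after Day 52 are handled is a matter of detail and is not part of this point.

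**Conclusion.** The point holds for Part 1. On the text available, nominally 9 of the 30 post-dose window days (8 to 10 with the visit window) have no scheduled contact, and events starting on Days 23 to 31 would be known only if volunteered. The consequence is less complete ascertainment of a primary safety endpoint late in the window.

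Three stronger readings should be resisted:
- **That 30% of events are lost.** The percentage counts calendar days. The documents give no event rate by day, so the number of events affected is unknown.
- **That the comparison with placebo is biased.** Active and placebo subjects in a cohort follow the same schedule under blinding, and nothing shows differential reporting.
- **That antibody-related reactions will fall in the gap.** Section 6.5 names the consequences of anti-drug antibodies as a major risk, and Section 5.3.1.1 reports antibody-positive monkeys from 336 to 672 hours. That was weekly repeat dosing in another species and does not fix the timing in humans after one dose.

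The conclusion assumes that the eCRF schedule adds no contact after Day 22. If it does, the remaining task is to show that contact in Appendix 2. Severity is minor to moderate; confidence is medium.

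**What to change.** Reconcile Sections 13.1 and 13.3 with Appendix 2 for Part 1. The choice between two routes is the sponsor's.

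- **Option (a): keep the 30-day window.** Add one telephone adverse event query at about Day 31 to Appendix 2. A call made earlier would leave the days after it uncovered. The cost is one call per Part 1 subject: 5 × 8 = 40 planned, and at most 40 + 5 × 2 = 50 with replacements (Section 8.4). The synopsis duration would change from 7 to about 8.3 weeks, and Section 10.3.6 would need to name the call as the last scheduled contact.
- **Option (b): keep the visit schedule.** State that Part 1 events are actively ascertained through Day 22, and use that window for the Part 1 treatment-emergent summaries. This changes wording only. Its small downside is that Part 1 would summarise 21 post-dose days against at least 30 days after the last dose in Part 2, so incidence in the two parts would rest on different windows, and the tables should say so.

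Under either option, put the chosen window into the Reporting and Analysis Plan before database lock. If the eCRF already holds a later query, showing it in Appendix 2 is enough. Reporting of serious events and events of special interest need not change.
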